7.8 Sample Size Considerations Primary Objective: Composite Endpoint Element

Since the primary objective is composite multiple endpoints will be determined. Each endpoint will have different requirements on the Study sample size determination. The contribution of various endpoints to sample size is tabulated in Table 7.8-1. The specific analyses are discussed in Sections 7.81 - .

Table 7.8-1 Sample Size Estimates for Pharmacodynamic Endpoints (all 80% power, alpha ≤0.025)

CONFIDENTIAL

RVNA GMC	Priority	Sample Size total 1:1	Mean ratio SYN/HRIG	Margin	CI	CV %
Superiority Study Day 8	Primary	<10	>10.0	10%	95	16.11
Non inferiority Study Day 99 GMC	Primary	138	0.88	20%	95	17.00
Non inferiority Study Day 99 percent subjects ≥ 0.5 IU/mL	Primary	72	1.0	10%	95	NA
Superiority Study Day 3	Secondary	<10	>10.0	10%	95	9.83
Superiority AUEC ₁₋₁₅	Secondary	320	1.45	10%	90	108.78

7.8.1 Superiority of Geometric Mean of RVNA Study Day 8

Superiority test for the ratio of two geometric means is used for determining the sample size. The null hypothesis is that the ratio for the two treatments is less than the defined margin that is expressed as:

$$H_0: \emptyset \leq \emptyset_L \text{ where } \emptyset_L > 1$$

Where, $\emptyset = \frac{GM_{SYN023}}{GM_{HRIG}}$; GM is the geometric mean.

The alternative hypothesis for superiority is expressed as: $H_1: \emptyset > \emptyset_L$. The ratio of superiority is more than ten-fold. The sample size required for this comparison is less than 10.

7.8.2 Non-inferiority of Geometric Serum RVNA on Study Day 99

The timepoint selected for non-inferiority in the current trial is based on need for a “later” timepoint at which to evaluate vaccine immunogenicity is from historical data from protocol SYN023-002 for which there are Study Day 84 and Study Day 112 timepoint (Table 7.8.2-1). The Study Day 99 is selected as being between these timepoints and closest for estimation.

The 20% margin was selected since it is a recommended bioequivalence margin for a lower bound of 0.8 (FDA 2001). Applying this margin to historical data near the Study Day 99 timepoint shows RVNA concentrations both well above the 0.5 IU/mL and should provide protective concentration in all subjects (Table 7.8.2-1).

Table 7.8.2-1 RVNA Historical Values by Timepoint for SYN023-002 Protocol

Visit	SYN023			HRIG		
	N	Geometric Mean	95% CI	N	Geometric Mean	95% CI
Day 42	73	8.05	(6.58, 9.85)	76	9.18	(7.91, 10.66)
Day 84	72	2.33	(1.79, 3.03)	75	2.75	(2.27, 3.33)

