Day 112	73	1.43	(1.09, 1.87)	76	1.71	(1.38, 2.11)

Non-Inferiority test for ratio of two geometric means is used for determining the sample size. The null hypothesis is that the ratio for the two treatments is less than the defined margin which is expressed as:

$$H_0: \emptyset \leq \emptyset_L \text{ where } \emptyset_L < 1$$

The alternative hypothesis for superiority is $H_1: \emptyset > \emptyset_L$. The calculated ratio between SYN023/RIG and the 95% confidence intervals for the ratio are presented in Table 7.8.2-2 and were used as inputs for the sample size calculation in PASS 15 software.

Table 7.8.2-2: Ratio (SYN023/HRIG) and 95% Geometric Confidence Intervals for Each Time-point for RVNA from SYN023-002 Protocol, Historical Data

Time Point	Ratio (SYN023/HRIG) for RVNA- SYN023-002	95% Geometric Means Ratio CI		CV
Day 35	81.28%	62.19%	106.23%	13.59%
Day 42	88.94%	68.79%	114.99%	13.04%
Day 84	88.50%	64.04%	122.30%	16.47%
Day 112	86.94%	61.88%	122.15%	17.32%

The sample size is calculated at 80% power with 20% margin of non-inferiority and equal allowance (number of subjects in group 1 = number of subjects in group 2) and alpha is taken to be 0.025.

The non-inferiority of serum GMC RVNA on study day 84 in SYN023 recipients (above) with respect to HRIG recipients would require the sample size of 138 for 80% power with an expected true geometric means ratio 88.00%. Note that based on historic data from protocol SYN023-002 the geometric ratio from Study Day 42 through Study Day 112 is stable and therefore it is expected that a true ratio of 88.00% is reasonable to determine non-inferiority at Study Day 99.

7.8.3 Non-inferiority of Percentage of Subjects with Serum RVNA ≥ 0.5 IU/mL on Study Day 99

20 % margin of noninferiority was selected since it is a recommended bioequivalence margin for a lower bound of 0.8 (FDA 2001). Historical SYN023 data is presented In Table 7.8.3-1.

Table 7.8.3-1 Historical Percentage of Subjects with RVNA ≥ 0.5 IU/mL

DAY	SYN023 + Vaccine		RIG + Vaccine	
	≥ 0.5 IU/mL Count (percentage)	Total	≥ 0.5 IU/mL Count (percentage)	Total
0	3 (4.0%)	75	1 (1.3%)	76
1	67 (90.5%)	74	1 (1.3%)	75
3	74 (98.7%)	75	1 (1.3%)	76
7	75 (100.0%)	75	6 (7.9%)	76
14	75 (100.0%)	75	75 (98.7%)	76
28	75 (100.0%)	75	76 (100.0%)	76
35	74 (100.0%)	74	74 (100.0%)	74
42	73 (100.0%)	73	76 (100.0%)	76
84	72 (100.0%)	72	75 (100.0%)	75
112	70 (95.9%)	73	75 (98.7%)	76

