The alternative hypothesis (H_a) is that the SYN023 vaccine is non-inferior to HRIG by a 20% margin.

$$H_a: \emptyset = \frac{GMC_{SYN023}}{GMC_{HRIG}} > 0.8$$

The null hypothesis is:

$$H_0: \emptyset = \frac{GMC_{SYN023}}{GMC_{HRIG}} \leq 0.8$$

The null hypothesis will be rejected at a significance level of 2.5% ($\alpha = 0.025$) if the lower bound of the one-sided 97.5% confidence interval for the GMC ratio is greater than the non-inferiority bound 0.8. Descriptive statistics will be displayed in a summary table following the same presentation for Section 8.1.1.1.

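### Protocol 7.8.2 gives two conflicting sets of historical GMC ratios; the assumed 0.88 follows one and is optimistic against the other, and the power for the Day 99 GMC element must be restated with a between-subject SD

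*Protocol*

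**What the plan says.** Protocol 7.8.2 takes its planning values from study SYN023-002. Table 7.8.2-1, titled "RVNA Historical Values by Timepoint for SYN023-002 Protocol", lists each arm's GMC with a 95% confidence interval. Table 7.8.2-2 lists SYN023/HRIG ratios with 95% intervals and a CV, and the text names these as the inputs to the sample-size software.

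The protocol then argues that "the geometric ratio from Study Day 42 through Study Day 112 is stable and therefore it is expected that a true ratio of 88.00" per cent is reasonable for Study Day 99. It concludes that the comparison "would require the sample size of 138 for 80% power with an expected true geometric means ratio 88.00" per cent. The design settings are given as "The sample size is calculated at 80% power with 20% margin of non-inferiority and equal allowance", with alpha 0.025. The summary row in Table 7.8-1 reads "Non inferiority Study Day 99 GMC Primary 138 0.88 20% 95 17.00", the last figure being the CV in per cent.

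SAP 8.1.1.2 rejects the null hypothesis "if the lower bound of the one-sided 97.5% confidence interval for the GMC ratio is greater than the non-inferiority bound 0.8". SAP 8.1.1.1 defines each GMC as the n-th root of the product of the values and names no covariates.

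The 138 does not set the size of the trial. Protocol 2.3 derives 320 per-protocol subjects (368 enrolled in the NRG) from the AUEC1-15 secondary endpoint.

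**The concern.** Two tables from one study, a page apart, should yield the same ratio on the same day, and these do not. The assumed 0.88 agrees with the table named as the input. It lies above what the GMCs themselves give around Study Day 99.

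The difference looks small but sits close to the margin. On the log scale the distance to the 0.80 bound is ln(0.88/0.80) = 0.0953, against ln(0.842/0.80) = 0.0512. That is a little over half, and required N goes with the inverse square of this distance.

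The element is one of four primary elements joined by AND in Protocol 2.1, so failing it fails the primary objective. A reader who wants to know how likely that is cannot rely on the stated 80% power.

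**Working it through.** **1. Ratios from the two tables.**

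| Day | Table 7.8.2-1 quotient | Largest value rounding allows | Table 7.8.2-2 |
|---|---|---|---|
| 42 | 8.05/9.18 = 0.877 | 0.878 | 0.889 |
| 84 | 2.33/2.75 = 0.847 | 0.851 | 0.885 |
| 112 | 1.43/1.71 = 0.836 | 0.842 | 0.869 |

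The third column is (SYN023 GMC + 0.005)/(HRIG GMC − 0.005). All three rows conflict beyond rounding.

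**2. Value at Study Day 99.** The historical study counts from Day 0 (Table 7.8.3-1), so Study Day 99 is Day 98, midway between Days 84 and 112. Log interpolation is then the geometric mean of the two neighbours:
- Table 7.8.2-1: √(0.8473 × 0.8363) = 0.842
- Table 7.8.2-2: √(0.885 × 0.8694) = 0.877

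Reading the day as 99 instead gives 0.841 and 0.877. The assumed 0.88 is close to the second figure and slightly above it.

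**3. The plan's own N.** Inputs are ratio 0.88, bound 0.80, CV 17%, one-sided alpha 0.025, power 80% and 1:1 allocation. The log SD is √ln(1 + 0.17²) = 0.1688. The normal approximation is

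N = 4(1.960 + 0.842)² × 0.1688² / ln(0.88/0.80)² = 98.5,

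which is 100 with equal whole arms; the noncentral t gives 102. The stated 138 does not follow from these inputs and would carry about 91% power. Exactly 138 comes from the Day 112 row of Table 7.8.2-2 (ratio 0.8694, CV 17.32%, 80% power, noncentral t). It also comes from 0.88 with CV 17.32% at 90% power by the normal approximation. The documents do not say which, if either, was used.

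**4. Effect of the ratio alone, CV kept at 17% (noncentral t).**

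| True ratio | Total N for 80% | Power at 320 |
|---|---|---|
| 0.88 | 102 | 99.9% |
| 0.847 | 278 | 85% |
| 0.842 | 344 | 77% |
| 0.836 | 464 | 64% |

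With 138 subjects, power at 0.842 is 42%.

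**5. What the 17% is.** The SE of the log ratio can be recovered from the Table 7.8.2-2 intervals as (ln upper − ln lower)/(2t). This gives 0.164 on Day 84 and 0.172 on Day 112. Converted by √(exp(SE²) − 1), these are 16.5% and 17.3%, matching the tabulated CVs of 16.47% and 17.32%. The 17% therefore describes the precision of a ratio estimated from about 147 to 149 subjects. It is not the variation between subjects.

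**6. Between-subject SD.** From the Table 7.8.2-1 intervals, each arm's log SD is √n × (ln upper − ln lower)/(2t). The Day 84 row, "Day 84 72 2.33 (1.79, 3.03) 75 2.75 (2.27, 3.33", gives 1.12 for SYN023 and 0.83 for HRIG, pooled 0.98. Day 112 gives a pooled 1.05.

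**7. Effect with a log SD of 1.0.** Total N for 80% power is about 3,460 at 0.88 and about 12,000 at 0.842. Power at 320 is about 13% and 7%. Over the SD range 0.98 to 1.05, power is 12.5% to 13.7% at 0.88 and stays between 6% and 7% at 0.842.

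**The case against.** Much can fairly be said for the plan.

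- **0.88 has a source.** A reader might infer that it is unsupported. It is not: Table 7.8.2-2 is the declared input and interpolates to 0.877.
- **Neither table can be shown to be wrong.** A reader might infer that 0.84 is the correct planning value. The documents do not say whether Table 7.8.2-2 comes from an adjusted model or a different subject set. On Days 84 and 112 its SEs match the unadjusted ones (0.164 and 0.172, against 0.163 and 0.172), but on Day 42 they do not (0.130 against 0.126). A matching SE rules out a gain in precision, not a shift in the estimate. If both US vaccines were used in that study, which is an assumption, adjusting for vaccine could shift it.
- **A decline is not established.** The Table 7.8.2-1 ratios fall by about 0.04, while each log ratio has an SE of 0.13 to 0.17. Noise could produce this. The same imprecision means that stability is not shown either.
- **The ratio's effect on this trial is limited at the plan's CV.** Enrolment rests on AUEC1-15, not on 138. At 320, power is still 85% at 0.847 and drops just under 80% only near 0.842.
- **The very low power figures come from the SD.** Even with the sponsor's 0.88, power is 13% once a between-subject SD is used. They are not evidence about the ratio.

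These points all stand. They do not remove the contradiction between the tables. Nor do they alter that the quotient of raw GMCs, which is what Table 7.8.2-1 gives, is the statistic the SAP tests.

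**Conclusion.** The contradiction is real, and 0.88 is optimistic against the planned statistic, although it follows from the declared input. At the plan's own CV, the step from 0.88 to 0.842 multiplies the required N by about 3.4 (344/102). It takes power at 320 per-protocol subjects from 99.9% to 77%, below the 80% stated for this element.

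Those two power figures are only a like-for-like comparison, because the 17% is not a between-subject CV. Power worth reporting is about 13% at 0.88 and 7% at 0.842. This assumes a log SD of about 1.0 carried over from SYN023-002, a common SD in the two arms, 160 evaluable subjects per arm and the unadjusted log-scale comparison. Correcting the ratio alone and keeping 17% would leave the power statement invalid.

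Which table is right remains open.

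**What to change.** In Protocol 7.8.2:
1. State how the Table 7.8.2-2 ratios were obtained (model, covariates, subject set), or correct them, so that the two tables agree.
2. Justify the stability statement with the uncertainty shown, or remove it.
3. Reconcile the stated 138 with its stated inputs, which give 102.
4. Replace the 17% with a between-subject log SD, about 1.0 from the Table 7.8.2-1 intervals, and carry the change into Table 7.8-1.
5. Restate power for this element at 320 per-protocol subjects under both 0.88 and 0.84. Show 0.84 beside 0.88 and do not impose it as the sole base case while the tables remain unreconciled.

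The cost is recalculation and rewording, and a stated power for a primary element that will be much less favourable.

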7.8.4 Superiority of Secondary endpoint AUEC1-15

$H_0: \emptyset \leq \emptyset_L$ where $\emptyset_L > 1$

Where, $\emptyset = \frac{GM_{SYN023}}{GM_{HRIG}}$; GM is the geometric mean.

The alternative hypothesis for superiority is expressed as: $H_1: \emptyset > \emptyset_L$.

The calculation of the sample size requires defining the range of the true mean ratio [AUEC₁₋₁₅ (SYN023/RIG): 147.55%, 90% CI: 115.10%, 189.14%], margin of superiority [10%], power [80%], coefficient of variation [CV: 108.78%] and alpha [0.025]. The calculation is done in PASS 15 software for the defined range of the true mean ratio and the results are presented for only those values for which the sample size is considered feasible.

A true AUEC₁₋₅ geometric mean ratio of SYN023/ HRIG of at least 1.45 and 80% power would therefore require a sample size of 320 with equal number of subjects in two groups for detecting the superiority with 10% of margin. Based on a true geometric mean ratio of at least 1.45, a total sample size of 320. A higher total sample of 368 allows for drop-outs and lost to follow up.

7.8.5 Absence of Rabies:

Synermore estimates that any PEP failure rabies cases occurring in the trial will be more likely due to a failure of clinical management or failure to follow protocol specified procedures or less likely intrinsic resistance to post-exposure prophylaxis. Synermore estimates this possibility of rabies at approximately 0.1% to 0.01%. This means there is a small chance of a single case of confirmed rabies occurs in the 184 subjects in the SYN023 NRG group. If one case of PEP failure occurs the point incidence of PEP failure will be 0.6% and the 95% confidence interval will extend from 0% to 2.0%. A 0.6% failure rate is high enough to be evidence of lack of efficacy and thus a failure of the primary objective.

7.9 Plan for Statistical Summaries and Analyses

7.9.1 Preliminary Data Reviews

A preliminary blinded data review of RVNA immunogenicity data may be performed following completion of immunogenicity assessments through Study Day 365. This review may present

individual and aggregate (mean or median [95% CI], as appropriate) RVNA immune response data, as well as change from pre-Study Drug to each post-Study Drug time point by individual or in aggregate. Study procedures and monitoring practices will not change following this preliminary review. No decision cut points or stopping rules will be stipulated. No hypothesis testing will be performed.

A preliminary unblinded review of RVNA immune response and safety data will be conducted following completion of Study Day 365. The database will be locked and the study will be unblinded for the preparation of this review. The purpose of this review is to obtain preliminary immunogenicity and safety data for use in the decision-making process regarding Study Drug dose level and dosing regimens to be employed in future studies of the Study Drug. This review will include all safety data, immune response data, clinical assessments, and concomitant medications through Study Day 365. Study procedures and monitoring practices will not change following this preliminary review. No decision cut points or stopping rules will be stipulated. No hypothesis testing will be performed. Personnel at the research site and at the immunology laboratory will remain blinded to all study results and to treatment assignments until after the Study Day 365 data have been collected, reviewed and queries resolved.

7.9.2 Final Study Report

The final study report will include all available safety data, immunogenicity data (including exploratory analyses), clinical assessments, and concomitant medications through the final study visit. The database will be locked prior to preparation of the final study report when all of the above data have been entered, reviewed, and all queries related to the data have been addressed.

Modifications or additions to the analyses described above will be included in the relevant statistical analysis plan(s). Any decisions to deviate from the planned analyses described in the protocol and in the statistical analysis plan will be described in detail in the final study report.

7.10 Computer Methods

Statistical analyses will be performed using SAS® version 9.1 or later under a Windows operating system.

8 DATA COLLECTION, MONITORING, AND RECORD RETENTION

For the purpose of monitoring and auditing the study, source documentation will consist of existing medical records and/or study records developed and maintained by the investigator. Any source document templates provided by the sponsor or its designee will serve as supplements to the subject's study record.

Data recorded on source documents will be transcribed onto case report forms (CRFs) provided by the sponsor or entered using electronic case report forms (eCRFs) using an Electronic Data Capture (EDC) system provided and approved by the sponsor. Completed, original CRFs will be retrieved by the sponsor or its designee and a copy of each completed CRF will be retained at the clinical site as part of the study records.

The study will be monitored regularly by the sponsor or its designee throughout the study period. For studies of unapproved investigational products, all study records (source documents, signed informed consent forms, copies of CRFs, IRB/IEC correspondence and approval letters, Study Drug management records) will be kept secured for a minimum of 2 years following the marketing of the investigational product or for 2 years after the discontinuation of the IND (or CTA, etc.). The investigator will ensure that study records are not disposed of or removed from the clinical site without prior notification and approval from the sponsor or its designee.

9 HUMAN SUBJECTS

9.1 Ethics and Regulatory Considerations

The study will be conducted according to the ethical principles set forth in the Declaration of Helsinki, ICH-GCP, Protection of Human Subjects (21 CFR 50), Institutional Review Boards (21 CFR 56), Obligations of Clinical Investigators (21 CFR 312), and local regulatory requirements.

The protocol and the informed consent document will be reviewed and approved by the IRB or IEC of each participating clinical site prior to any protocol-specified procedures being conducted. All documents given to the subject will be reviewed and approved by the IRB/IEC. The investigator will inform the IRB/IEC as to the progress of the study on a regular basis, or at minimum, once a year. The sponsor will keep the IRB informed of the progress of the study.

Written informed consent will be obtained from each subject prior to any protocol-specified procedures being conducted.

To maintain confidentiality, subject identification numbers will be used to identify the subject's laboratory specimens, source documents, CRF, study reports, etc. All study records will be maintained in a secured location. Clinical information will not be released without written permission from the subject except as necessary for monitoring or auditing of the study by the sponsor or its designee or applicable regulatory authorities. Personal information may be difficult to remove from safety information but this data is kept under additional measures of data protection and is not part of the study database.

After the study has been unblinded, the subject should be informed by letter which treatment (SYN023 or HRIG) the subject received. The text of this letter will be submitted and approved by the relevant IRB/IEC before issuance to subjects.

9.2 Institutional Review Board or Independent Ethics Committee

All the documents the IRB/IEC may need to fulfill its responsibilities, such as the protocol, protocol amendments, information concerning subject recruitment, payment or compensation procedures, etc., will be submitted to the IRB/IEC by the investigator. The IRB's/IEC's written, unconditional approval of the study protocol and the informed consent form will be in the possession of the investigator/clinical site staff prior to the conduct of any protocol-specified procedures.

Modifications other than administrative changes and typographical errors in the protocol may not be implemented without prior written IRB/IEC approval (except when necessary to eliminate immediate hazards to the subjects) or when the modification involves only logistical or administrative aspects of the study. Such logistical or administrative modifications will be submitted to the IRB/IEC in writing by the investigator, and a copy of the correspondence to verify the submission will be maintained.

The investigator must inform the IRB/IEC of modifications to the informed consent form or any other documents previously submitted for review/approval, of any new information that may adversely affect the safety of the subjects or the conduct of the study, provide an annual update and/or request for re-approval, and advise the IRB/IEC when the study has been completed.

Any documents or forms to be provided to the subject (e.g., information cards, form letters from the investigator), and all forms of study advertising (flyers, brochures, print advertisements, radio or television scripts, etc.) must be approved by the sponsor or its designee prior to the clinical site submitting them to the IRB/IEC. Approval from the IRB/IEC must be obtained prior to providing the documents or forms to the subject.

9.3 Informed Consent

The principles of informed consent in the current edition of the Declaration of Helsinki and ICH-GCP/21 CFR 50.25 should be implemented prior to any protocol-specified procedures being conducted. Informed consent will be documented in writing on a consent form approved by the IRB/IEC.

All relevant information should be provided in both oral and written form in a way that is understandable to the subject. Ample time and opportunity must be given for the subject to inquire about details of the study. The written consent document will embody the elements of informed consent as described in the Declaration of Helsinki and will also comply with local regulations.

The investigator or the investigator's qualified designee will explain the nature of the study and inform the subject that participation is voluntary and that the subject can leave the study at any time, without penalty or loss of benefits to which they are otherwise entitled. The subject must be informed about the study's purpose including why the subject was selected to participate, study goals, expected benefits and risks, potential risks, and that some potential risks are unforeseeable. The subject must be provided with a description of the procedures and the estimated duration of time required for participation in the study, as well as alternative interventions or courses of treatment, if applicable.

The subject must receive an explanation as to whether any compensation and any medical treatments are available if injury occurs and, if so, what they are, where further information may be obtained, and who to contact in the event of a study-related injury. Subjects must be told who to contact for answers to any questions related to the study. The extent of the confidentiality of subject records must be defined and the subject must be informed that applicable data protection legislation applies.

The subject must be informed that the monitor(s), auditor(s), IRB/IEC members, and the applicable regulatory authorities will be granted direct access to the subject's original study medical records for verification of protocol-specified procedures and/or data, without violating the confidentiality of the subject to the extent permitted by the applicable laws and regulations. The subject must be informed that his/her signature on the informed consent form indicates that he/she has decided to participate in the study, having read and discussed the information presented.

Modifications made by the investigator to an informed consent form template provided to the investigator by the sponsor or its designee will be reviewed and approved by the sponsor.

The original, signed informed consent form for each subject will be maintained by the investigator as part of the subject's study records. A copy of the signed informed consent form will be provided to each subject.

